1 STUDY OBJECTIVES AND ENDPOINTS

The purpose of this statistical analysis plan (SAP) is to describe the safety, tolerability, efficacy and pharmacokinetic to be included in the Clinical Study Report for Protocol RD.06.SPR.18250.

1.1 Study Objective (s)

1.1.1 Primary objective (s)

The primary objective of this study is to determine the safety of CD5789 50 µg/g cream in the long-term treatment (up to 52 Weeks) of subjects with acne vulgaris.

1.1.2 Secondary objective (s)

Efficacy will be evaluated as a secondary objective.

2 STUDY DESIGN

This is a multi-center, open-label, non-comparative safety and efficacy study with 52 Weeks of treatment on the face and trunk for acne vulgaris.

Male and female subjects, 9 years of age or older, with an IGA of 3 and a minimum of 20 inflammatory lesions and 25 non-inflammatory lesions on the face, with a PGA of 3 and a minimum of 20 inflammatory lesions and 20 non-inflammatory lesions

on the trunk will be enrolled in the study (PGA and truncal lesions are optional inclusion criteria for children between 9-11 years old).

Approximately 450 subjects will be enrolled worldwide (Europe, USA). The total number of sites is expected to be approximately 30 to 40 with a minimal of 10 subjects per site.

3 EFFICACY AND SAFETY ASSESSMENT

Refer to Protocol Section 7 “Clinical Trial Assessment” for details.

3.1 Efficacy assessment

Efficacy will be evaluated as a secondary objective in this study.

3.1.1 IGA (Investigator’s global assessment) of facial acne

The areas defined for IGA assessment are forehead, each cheek, chin and nose. IGA will be confined to a global assessment of each area. The Investigator’s Global Assessment (IGA) is a snapshot static assessment.

Investigators will evaluate the facial acne at Screening, Baseline, and at Week 12, Week 20, Week 26, Week 38 and Week52/ET visits or any unscheduled visit, according to the following scale:

Investigator’s Global Assessment Scale (IGA) Face		
0	Clear	Clear skin with no inflammatory or non-inflammatory lesions.
1	Almost Clear	A few scattered comedones and a few small papules.
2	Mild	Easily recognizable; less than half the surface is involved. Some comedones and some papules and pustules.
3	Moderate	More than half of the surface is involved. Many comedones, papules and pustules. One nodule may be present.
4	Severe	Entire surface is involved. Covered with comedones, numerous papules and pustules. Few nodules may be present.

Note: IGA assessment is to be done prior to lesion counts

3.1.2 PGA (Physician Global Assessment) of truncal acne

The areas defined PGA assessment are shoulders, upper back and anterior chest which are accessible to self-application by the subject, i.e. the regions that the subject can easily reach and apply the study drug by himself or herself. PGA will be confined to a global assessment. The PGA is a snapshot static assessment.

Investigators will evaluate the upper truncal acne at Screening, Baseline, and Weeks 12, Week 20, Week 26, Week 38 and Week 52/ET visits or any unscheduled visit, according to the following scale.

Physician Global Assessment Scale (PGA) Trunk		
0	Clear	Clear skin with no inflammatory or non-inflammatory lesions.
1	Almost Clear	A few scattered comedones and a few small papules.
2	Mild	Easily recognizable; less than half the surface is involved. Some comedones and some papules and pustules.
3	Moderate	More than half of the surface is involved. Many comedones, papules and pustules. One nodule may be present.
4	Severe	Entire surface is involved. Covered with comedones, numerous papules and pustules. Few nodules may or not be present.

Specific requirements for children between 9 and 11 years old who do not have moderate acne on the upper truncal region at Baseline (i.e. who do not have PGA of 3, at least 20 inflammatory lesions on the trunk and at least 20 non-inflammatory lesions on the trunk):

The PGA scale will be completed at all visits (including Week 1, 2, 4 and 8 visits), and used by the investigators to decide if they want to start the treatment for truncal acne. However, the PGA data from these subjects will not be analyzed.

Note: PGA assessment is to be done prior to lesion counts.

3.1.3 Subject self-assessment of facial acne improvement

Subject self-assessment should occur prior any investigator assessment in order to not influence the subject. Subjects will evaluate his/her facial acne improvement by comparing what they recall on their disease at the start of the study at Weeks 12, 26 and 52/ET visits by completing the following scale:

Subject's Assessment of Acne Improvement	
0	Complete Improvement
1	Marked Improvement
2	Moderate Improvement
3	Minimal Improvement
4	No Change
5	Worse

3.2 Safety assessment

A safety assessment will be conducted for all subjects at the Screening visit (from the Informed consent signature) and every subsequent visit. The safety parameters are the recording of adverse events, laboratory safety tests, physical examination, vital signs and local tolerability scores on the face and on the trunk (0 [none] to 3 [severe]) for erythema, scaling, dryness, and stinging/burning.

3.2.1 Local tolerability assessment

Local tolerability (erythema, scaling, dryness, and stinging/burning) will be assessed on the face (forehead, each cheek, nose, chin) and trunk (upper trunk; middle and lower trunk will be captured if subject applied study drug on these areas) separately and will be graded separately at Baseline and at each post-baseline visit. Refer to protocol section 7.2.3 and 7.2.4 for more details.

Specific requirements for children between 9 and 11 years old who do not have moderate acne on the trunk at Baseline (i.e. do not have PGA of 3, at least 20 inflammatory lesions on the trunk and at least 20 non-inflammatory lesions on the trunk):

If the investigators decide to start the treatment for truncal acne in these subjects during the study, then the local tolerability scales (for trunk) will be completed and data will be evaluated in the safety analysis.

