5.2 Safety (SAFT) Population on the Trunk

The SAFT population is defined as any subjects in the SAF population who also applied the study medication on the upper truncal region and /or on the middle and lower back at least once.

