7 STATISTICAL METHODS AND DATA CONSIDERATIONS

For statistical analyses purpose, baseline is defined as the last measurement prior to the first application of the study drug.

No inferential statistical analysis is planned. Data to be collected will be summarized as observed.

For the summary statistics, the categorical variables will be summarized by frequency and percentage for each response category (N, %); and the continuous variables will be summarized using means, medians, minimum, maximum, and standard deviations.

All efficacy variables, DLQI/ C-DLQI, local tolerability, laboratory tests and vital signs will be summarized and analyzed by analysis visit. The methodology for defining analysis visit is provided in Section 7.9 “Analysis visit definition”.

SAS version 9.3 or above will be used for all statistical analyses.

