7.1.2 Demographic and baseline characteristics

The following demographics variables will be summarized for SAF population: Age, Ethnicity, Race, Skin phototype, and Gender. Age will be analyzed as a continuous variable and will be tabulated by age groups of “<18years” (“9-11 years”, “12-14 years”, “15-17 years”), “18-64 years” (“18-25 years”, “26-35 years”, “36-45 years”, “46-64 years”) and “≥65 years”.

Baseline IGA, PGA and Acne presence on back (middle/lower) will be summarized using SAF population. Facial lesion counts (inflammatory and non-inflammatory) will be summarized using SAF population and truncal lesion counts (inflammatory and non-inflammatory) will be summarized using SAFP population.

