7.5.2 Cutaneous safety

Analyses of the local tolerability on the face will be based on SAF population; and the analyses of the local tolerability on the trunk will be based on SAFT population.

Local tolerability variables (erythema, scaling, dryness, stinging/burning) will be summarized at Baseline, each post-baseline visit, "Worst" score, and "Final" score. "Worst" score is the highest severity score observed during post-baseline period for a subject. "Final" score is the last data observed during the post-baseline period for a subject. In addition, the number and percentage of subjects with a local tolerability score worsened from baseline will be summarized descriptively at each post-baseline visit, "Final" scores, and "Worst" score.

Additionally, subjects with a local tolerability score worse than the Baseline score will be summarized graphically at each post-Baseline visit including "Final" scores and "Worst" score.

Summary statistics by treating the severity scale as continuous outcome will also be presented.

Subgroup analyses by Age Group (<18 years, >=18 years), Race (white, non-white), Gender (female, male), Country (Europe, USA), and Skin Phototype (I-III, IV-VI) will be provided.

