7.9 Analysis visit definition

For efficacy, DLQI/ C-DLQI and local tolerability data, analysis visit will be assigned according to the algorithm in Table 3 below to summarize the data by proper visit window interval. Study day is calculated as visit date minus the date of first application plus 1. If multiple measurements are taken in the same interval, the one closest to the target study day will be used for the analysis. If two measurements are taken with equal differences in timing compared with the target date, the nominal visit number (recorded on the CRF page) will be used. If there is missing measurement at Baseline, Screening data will be used to impute the missing baseline data, i.e. Baseline will be the last available data prior to first application of study drug.

Table 3 Analysis Visit and Visit Window

Analysis Visit	Analysis Visit Number in Derived Dataset	Target Study Day	Visit Window (Study Day)
Baseline	1	1	[≤1]
Week 1	2	8	[2 – 11]
Week 2	3	15	[12 – 21]
Week 4	4	29	[22 – 42]
Week 8	5	57	[43 – 70]
Week 12	6	85	[71 – 112]
Week 20	7	141	[113 – 161]
Week 26	8	183	[162 – 224]
Week 38	9	267	[225 – 315]
Week 52	10	365	> 315

When assigning the analysis visits for vital signs, no visit window will be applied; Nominal eCRF visit will be used as analysis visit for summaries. Only data from schedule visit will be summarized.

When assigning the analysis visits for laboratory data, no visit window will be applied, however, the following rules will be applied:

1. If sample date is at or prior to date of first application, the data will be considered as screening visit. If multiple measurements of screening due to rescreening, retest or other unexpected reasons, the data closest to date of first application will be chosen.
2. Lab data from scheduled visit will be considered first when assigning analysis visit of each scheduled visit. If there is no data from scheduled visit available, the last of those corresponding unscheduled visit will be considered for assignment of analysis visits.
3. When assigning Final visit, the lab data from the last post-baseline scheduled visit during treatment period will be considered first. If the last scheduled visit during treatment period have missing lab data due to any reason and there are subsequent unscheduled lab data available, the last of those corresponding unscheduled lab data will be assigned as Final visit. Otherwise, the previous visit lab data will be considered in the same manner.

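### For a trunk area first treated after Day 1, the SAP's single study baseline and pooled Trunk tables do not give a like-for-like measure of worsening in local tolerability

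*SAP*

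**What the plan says.** - **Capture (SAP 3.2.1).** Erythema, scaling, dryness and stinging/burning are scored on the face and on the trunk. The upper trunk is always in scope; "middle and lower trunk will be captured if subject applied study drug on these areas". The same sentence says that face and trunk are assessed "separately and will be graded separately at Baseline and at each post-baseline visit". For children aged 9 to 11 without moderate truncal acne at Baseline, the trunk scales are completed if the investigator starts truncal treatment during the study, and those data go into the safety analysis.
- **Baseline (SAP 7 and 7.9).** Section 7 states that "baseline is defined as the last measurement prior to the first application of the study drug". Section 7.9 counts study days from first application, closes the Baseline window at day 1, and falls back on Screening data if Baseline is missing.
- **Population (SAP 5.2).** SAFT takes any SAF subject who "applied the study medication on the upper truncal region and /or on the middle and lower back at least once".
- **Analysis (SAP 7.5.2 and 9).** Besides raw severity, "the number and percentage of subjects with a local tolerability score worsened from baseline will be summarized descriptively at each post-baseline visit", and also for the Final and Worst scores. Section 9 lists one Trunk table per sign, with none split by trunk region.

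**The concern.** Worsening from baseline means something only if both scores describe the same skin and the first was taken before that skin was treated. The SAP uses one baseline date for the whole body, but it lets the treated and scored part of the trunk grow during the study. For subjects whose trunk area is first treated after Day 1, the reported change may compare different areas, use a baseline from long before treatment of that area, or have no baseline.

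Safety is the primary objective, and local tolerability is the first safety endpoint listed in section 4.2. The trunk worsening tables are a main place where a reader would look for irritation on the back.

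**Working it through.** The SAP states no figure for this point, so the check sets the rules side by side.

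**1. Is baseline region-specific?** No. Section 7 refers to the first application of study drug without naming a region. Where the SAP does spell out a first application, for treatment duration in 7.5.1.2, it takes the earlier of face and trunk. A subject who treats the face on Day 1 has therefore used up the baseline for every region.

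**2. Follow a late starter through 7.9.** Suppose treatment of the middle/lower back begins at the Week 8 visit, study day 57, and the site scores the back just before the first application there. Day 57 falls in the window 43 to 70, so the score becomes the Week 8 post-baseline value. It describes untreated skin, yet it can enter the Week 8 and Worst summaries. The only value that can serve as baseline is one from day 1 or before, at least 57 − 1 = 56 days earlier, if it exists.

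**3. Does it exist?** Section 3.2.1 schedules grading at Baseline but makes middle/lower scoring conditional on use there. A subject with no plan to treat the back on Day 1 may have no score. The Screening fallback is unlikely to help. Section 3.2 lists tolerability among the safety parameters in general terms, but 3.2.1, the specific text, schedules grading from Baseline onward. Children aged 9 to 11 who start truncal treatment mid-study are in the same position for the whole trunk: 5.2 puts them in SAFT, possibly without a trunk score before first application of the drug.

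**4. Does it matter whether the trunk has one grade or several?** Not for this point.
- If there is one trunk grade and its area grows when the back is treated, follow-up covers more skin than baseline did.
- If regions are graded separately, the late-treated region lacks a usable baseline, and nothing says which score enters the Trunk table. The selection rule in 7.9, "If multiple measurements are taken in the same interval, the one closest to the target study day will be used for the analysis", cannot separate two scores from the same visit, and neither can its tie-break on nominal visit number.

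**5. Who is in the denominator?** Sections 7.4.3 (IGA change), 7.5.4 (laboratory shifts) and 7.8 (DLQI) each require both a baseline and a post-baseline value. Section 7.5.2 sets no such condition for worsening, so the handling of subjects without a regional baseline is open.

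**6. Illustration of sensitivity to the combining rule, on assumed inputs only.** Let p be the worsening rate in each region and s the share of subjects with a middle/lower score. Using the upper trunk alone gives p. Taking the worse of two independent regions gives p + s × p × (1 − p).

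| p | Upper only | s = 0.2 | s = 0.5 | s = 0.8 |
|---|---|---|---|---|
| 0.10 | 10% | 11.8% | 14.5% | 17.2% |
| 0.20 | 20% | 23.2% | 28.0% | 32.8% |
| 0.40 | 40% | 44.8% | 52.0% | 59.2% |

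For example, 0.20 + 0.5 × 0.20 × 0.80 = 0.28. If the two regions always agree, every entry in a row equals p. The SAP gives neither p nor s, and it does not state a worse-of-two rule. The table shows only that the choice of rule can matter; it does not estimate a bias in this trial.

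**The case against.** The strongest case on the other side has four parts.

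- **Capture at Baseline.** A reader might infer that the middle/lower trunk is scored only once drug is already on it, so that nobody has a baseline there. The text does not say so. The sentence that sets the condition also schedules grading at Baseline, and section 7.1.2 shows that the back is looked at then: "Baseline IGA, PGA and Acne presence on back (middle/lower) will be summarized using SAF population". A subject due to treat the back from Day 1 may well have a valid score. This part stands, and it confines the point to areas first treated later.
- **One score or two.** A reader might infer two trunk scores per visit. The parenthesis in 3.2.1 may only define the area covered by a single trunk grade, as the facial list does for the face. This also stands: the number of scores is not established. Step 4 above does not depend on it.
- **Left to the protocol.** Section 3.2.1 says "Refer to protocol section 7.2.3 and 7.2.4 for more details", and those sections may settle when each area is scored. They were not available for this check. Baseline, denominator and tabulation, however, are analysis definitions that the SAP itself sets.
- **Small reach.** Entry requires moderate truncal acne except in children aged 9 to 11 (section 2), and 5.3 places the qualifying lesions on the upper trunk. Subjects who treat only the middle/lower back are therefore probably few. Raw severity tables and adverse event tables need no baseline, and no inference is planned. All of this stands and limits the consequence.

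**Conclusion.** The point holds for trunk areas first treated after Day 1. For these, the stated rules count a pre-application score as post-baseline or leave no baseline, and the pooled Trunk table mixes such subjects with the rest.

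It does not make the trunk endpoint invalid. Upper-trunk change in subjects graded there at Baseline is well defined.

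A reader might also set a 36% rate (1 − 0.8², the worse of two regions) against a 20% one-region baseline and call the gap false worsening. The SAP does not support that figure. It needs an assumed 20% rate, independence between regions and a maximum rule that the SAP never states, and it compares how common irritation is rather than change within subjects.

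The size in this trial cannot be computed from the SAP. It depends on how many subjects start a trunk area late and on the irritation rate in each region. The conclusion assumes that first application means first anywhere on the body, which is how section 7 reads and how 7.5.1.2 uses the term. The change should be made before the trunk tables are programmed.

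**What to change.** In 7.5.2 and section 9:

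1. Where regional scores are recorded, tabulate upper trunk and middle/lower trunk separately, each among subjects who applied drug to that region.
2. Define baseline for a region as the last score before first application to that region. Earlier scores are then not post-baseline for it.
3. Count worsening only in subjects with both a baseline and a post-baseline score for the region.
4. Report how many subjects lack a regional baseline, and show their scores in the raw severity tables only.

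Apply the same baseline rule to children aged 9 to 11 who start truncal treatment mid-study. Align 3.2.1 with protocol sections 7.2.3 and 7.2.4 so that a score is recorded before first application to a region where feasible.

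**Cost.** One more set of descriptive trunk outputs and a slightly smaller denominator. Section 9 lists four summary tables, four worsening tables, four subgroup tables and four figures for the trunk, so a full split adds at most 4 + 4 + 4 + 4 = 16 outputs. Splitting only the summary and worsening tables adds 8. The analysis needs the date of first use by region. Section 7.5.1.2 refers to face and trunk, but the SAP does not show whether the middle/lower trunk is dated separately. Separate tables cannot supply a baseline that was never recorded, which is why the number missing must be reported.

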3.2.2 Adverse events

Adverse events (AEs) are to be monitored throughout the course of the clinical trial. All AEs are to be reported on the Adverse Event Form of the eCRF with complete information as required, including onset/end dates of AEs, severity of AEs, relationship to the study drug, serious AEs and AEs of special interest.

3.2.3 Laboratory safety tests

The laboratory analyses will be based on Central laboratory results. The following laboratory safety tests will be performed at the Screening visit, Week 26 and Week 52/ET visits. Abnormal laboratory results will be evaluated by the investigator as clinically significant or non-clinically significant.

- Hematology: White blood cell (WBC) count with differential, red blood cell (RBC) count, hemoglobin(Hb), hematocrit (Hct), mean cell volume (MCV), and platelet count (Plt)
- Blood chemistry: Creatinine, uric acid, urea nitrogen, gamma glutamyl transferase (GGT or γ GTP), alkaline phosphatase (ALP), aspartate aminotransferase (ASAT=SGOT [AST in US]), alanine aminotransferase (ALAT=SGPT [ALT in US]), and bilirubin (total, direct & indirect).
- Urinalysis: blood, proteins, leukocytes, glucose

3.2.4 Vital signs

Evaluation of vital signs will be performed after approximately 5 minutes rest in the sitting

position at the Screening visit, Baseline visit and at Weeks 12, 26 and 52 /ET/Unscheduled visits. It will include measurement of systolic and diastolic blood pressure and pulse rate.

3.2.5 Physical examination

The investigator should evaluate following body systems as “normal” or “abnormal” and should also evaluate abnormal values as “clinically significant/not clinically significant” at the Screening visit, Baseline visit and at Weeks 12, 26 and 52 /ET and Unscheduled visit:

- Skin
- Lungs
- Abdomen
- Eyes/ears/nose/throat
- Neurological function
- Musculoskeletal system
- Lymph nodes
- Cardiovascular system

3.3 PK assessment (at selected sites)

In selected sites only, a PK (pharmacokinetic) assessment will be performed only in 9 to 11 year old subjects who have agreed in the parents/guardian ICF and Assent form to have a PK sample taken. Systemic exposure to CD5789 will be assessed at Week 4 visit in a single sample PK time point.

The following PK parameters will be determined for each subject if sufficient CD 5789 plasma concentrations are detectable (above the limit of quantification):

- C 4 hours
- Extrapolated AUC0-24h using the linear correlation between AUC0-24h and C 4 hours

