5 POPULATIONS ANALYZED

As this study is a long-term safety study, only the safety population will be used for all statistical analyses.

The safety (SAF) population will be used for the analyses of IGA data and all safety data except for the local tolerability on the trunk.

The safety population on the trunk (SAFT) will be used for the analyses of the local tolerability on the trunk.

The safety population for the PGA (SAFP) will be used for the analyses of the PGA data.

In the case that the SAFT turns out to be identical to the SAF population, then all safety analyses will be based on the SAF population. In the case that the SAFP turns out to be identical to the SAF population, then the analyses of all IGA and PGA data will be based on the SAF population.

PK evaluable subjects in the SAF population will be used for the analysis of PK data.

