5.1 Safety (SAF) Population

The SAF Population is defined as subjects who applied the study drug(s) at least once.

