7.7 Pharmacokinetic Analysis

Quantifiable PK profiles of CD5789 from previous PK studies 18237 and 40182 were used to investigate the relationship between AUC_{0-24h} and selected plasma points. A strong correlation was found between AUC_{0-24h} and C_{4h} using linear regression. The extrapolated AUC_{0-24h} will be calculated using the following equation. For more details, refer to the document *CD5789 Limited sampling strategy for estimation of the AUC_{0-24h} in the 9 to 11 years old subjects*.

$$AUC_{0-24h} = 34.26 + 7.90 * C_{4h}$$

The PK parameters C_{4h} and extrapolated AUC_{0-24h} will be summarized by descriptive statistics. Coefficient of variation (CV), geometric mean (GEO Mean), geometric standard deviation (GEO SD) and geometric coefficient of variation (GEO CV) will be presented as well.

For C_{4h} , the BLQ (below limit of quantification) values will be imputed using the LOQ (limit of quantification: 5pg/mL). Summaries with imputation and with no imputation will be both provided.

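### The Week 4 PK summary pools 9-11 year olds who may be treating the face only with those treating face and trunk, so it cannot show systemic exposure under face-plus-trunk use and may understate it

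*SAP*

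**What the plan says.** **Who is sampled, and when.** Under section 3.3, PK "will be performed only in 9 to 11 year old subjects who have agreed in the parents/guardian ICF and Assent form", at selected sites, and "Systemic exposure to CD5789 will be assessed at Week 4 visit in a single sample PK time point". The section sets no condition on the area being treated.

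**What these children may be treating.** Section 2 describes the study as "52 Weeks of treatment on the face and trunk for acne vulgaris", but adds that "PGA and truncal lesions are optional inclusion criteria for children between 9-11 years old". For children of that age without moderate truncal acne, section 3.1.2 has the PGA completed at every visit, including Weeks 1, 2, 4 and 8, and "used by the investigators to decide if they want to start the treatment for truncal acne". Section 3.2.1 likewise foresees that trunk treatment may begin during the study.

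**How PK is analysed.** Section 5 states: "PK evaluable subjects in the SAF population will be used for the analysis of PK data". Section 5.1 adds: "The SAF Population is defined as subjects who applied the study drug(s) at least once". One application anywhere is enough, and the SAP does not define what makes a subject PK evaluable. Section 7.7 plans a single set of descriptive statistics for C4h and extrapolated AUC0-24h, shown with and without imputation of BLQ values. Section 9 lists one PK summary table and one individual listing. Neither is split by treated area.

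**The concern.** PK is confined to the one age group whose members may, by design, be treating the face only when the sample is drawn. A child who starts the trunk after Week 4 contributes only a face-only concentration.

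For a topical product, a larger treated area would ordinarily be expected to bring higher systemic exposure. A pooled mean, geometric mean and CV may therefore combine two levels of exposure. A reader could not tell from it what exposure to expect in a child treating face and trunk, and the figure may be too low for that purpose. The CV would combine differences in treated area with ordinary between-child variability.

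This is the trial's only measure of systemic exposure. It is taken in the youngest subjects, and safety is the primary objective (section 1.1.1).

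The SAP recognises the mix elsewhere. The SAFT population (section 5.2) separates trunk users for trunk tolerability, the SAFP population (section 5.3) removes children without moderate truncal acne from the PGA analysis, and section 7.5.1.3 allows usage to be summarised separately for face and trunk. Only the PK summary has no such separation.

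**Working it through.** The SAP states no PK sample size or expected concentration, so there is no figure of its own to reproduce. The check is a mixture calculation for the arithmetic mean.

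**Inputs from section 7.7**
- AUC0-24h = 34.26 + 7.90 × C4h
- BLQ values of C4h are set to the LOQ, 5 pg/mL

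**Assumptions (the SAP gives none of these)**
- f = share of PK children treating only the face at Week 4: 0.25 to 0.75
- r = face-only C4h divided by face-plus-trunk C4h: 0.25 to 0.75
- Face-plus-trunk C4h = 20 pg/mL
- Imputed C4h values enter the AUC equation

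**Formulas**
- Pooled C4h = f × (face-only C4h, not below 5) + (1 − f) × (face-plus-trunk C4h)
- C4h ratio = pooled C4h / 20. When the LOQ does not bind, this equals 1 − f(1 − r).
- AUC ratio = (34.26 + 7.90 × pooled C4h) / (34.26 + 7.90 × 20), with denominator 192.26

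| f | r | Pooled C4h (pg/mL) | C4h ratio | Pooled AUC | AUC ratio |
|---|---|---|---|---|---|
| 0.25 | 0.75 | 0.25×15 + 0.75×20 = 18.75 | 0.938 | 182.39 | 0.949 |
| 0.25 | 0.50 | 0.25×10 + 0.75×20 = 17.50 | 0.875 | 172.51 | 0.897 |
| 0.50 | 0.50 | 0.50×10 + 0.50×20 = 15.00 | 0.750 | 152.76 | 0.795 |
| 0.50 | 0.25 | 0.50×5 + 0.50×20 = 12.50 | 0.625 | 133.01 | 0.692 |
| 0.75 | 0.25 | 0.75×5 + 0.25×20 = 8.75 | 0.438 | 103.39 | 0.538 |

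The first and last rows are the extremes: pooled C4h is 6% to 56% low and pooled AUC 5% to 46% low. AUC moves less because the intercept 34.26 does not shrink with C4h.

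**Where the effect shrinks or disappears**
- *Lower concentrations.* Take face-plus-trunk C4h = 10 pg/mL, f = 0.75, r = 0.25. The face-only value would be 2.5 but is set to 5. Pooled C4h is 0.75×5 + 0.25×10 = 6.25, ratio 0.625. The AUC ratio is 83.64/113.26 = 0.738. The C4h shortfall is 37.5%; without the LOQ rule it would be 56%.
- *All values at or below the LOQ.* Every C4h becomes 5, every AUC becomes 34.26 + 7.90×5 = 73.76, and both ratios are 1.00.
- *No face-only children (f = 0), or equal exposure (r = 1).* Both ratios are 1.00.
- *No-imputation summary.* If all face-only children are BLQ and drop out of it, its ratio is also 1.00.

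**The case against.** The strongest case against has four parts.

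**The direction is not demonstrated.** A reader might infer that the pooled means do understate face-plus-trunk exposure. That needs face-only children in the PK set and lower concentrations in them. The SAP documents neither, although the second is plausible from the smaller treated area. This stands: the supported wording is that the summary may understate exposure.

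**The protocol may settle it.** Evaluability rules are often left to the protocol, and the undefined term could restrict PK to trunk users. This stands as a possibility. But section 3.3 states who is sampled without any such condition, and how results are grouped is a matter for the SAP.

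**The SAP never says that the PK summary targets face-plus-trunk use.** Face-only treatment is part of planned use at ages 9-11, and a pooled summary correctly describes exposure as used. This also stands, and is why the pooled row should stay. It does not help a reader who needs exposure for the treated area named in the study design.

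**The SAP's own rules dampen the effect, and individual data are listed.** The AUC intercept and the BLQ rule do reduce the size, so a calculation strictly proportional to treated area would overstate the AUC effect. The PK listing allows partial recovery, but section 9 does not say that it shows treated area.

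Two further inferences go too far. The CV would not reflect area mix instead of between-child variability; it would reflect both. And PK is not the trial's only exposure information, since section 7.5.1 reports duration and usage; it is the only systemic measure.

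**Conclusion.** The point holds as a gap in the planned PK summary. By the SAP's own rules, children treating different areas can enter one pooled row, and nothing in section 7.7 or section 9 lets a reader separate them. The pooled C4h and AUC0-24h therefore cannot show exposure under face-plus-trunk use.

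Whether they understate it, and by how much, is not known. The range of about 6% to 56% for C4h and 5% to 46% for AUC rests wholly on the assumed face-only share, exposure ratio and 20 pg/mL level. Zero is also possible, and without a split the report would not show which case applies. The change should be made, but the SAP does not support a claim of established bias.

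**What to change.** - **Section 7.7 and the PK summary table in section 9:** add rows for C4h and extrapolated AUC0-24h by area treated up to the Week 4 sample (face only; face plus trunk), with n and BLQ count in each row. Keep the pooled row as descriptive.
- **Individual PK listing:** show the treated area and the trunk start date, so that children who had only just started the trunk can be seen.
- **Interpretation:** base any statement about face-and-trunk exposure on the face-plus-trunk row.
- **PK evaluable:** define the term in section 5, or point to the protocol definition.

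SAFT should not be used for the split. It counts trunk application at any time, so a child who starts the trunk after Week 4 would be put with the trunk users.

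The cost is some SAP wording and one stratified table, built from the face and trunk application dates that section 7.5.1.2 already uses. The downside is small numbers per row, in a group already limited to selected sites and consenting families. No treatment or sampling rule changes.
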